9.2.5.3. Clinical Chemistry

Clinical Chemistry Panel			
Blood Urea	Potassium	ALT	Albumin
Nitrogen			
Creatinine	Chloride	Gamma-Glutamyl Transferase	Total Protein
		(GGT)	
Glucose	Calcium	Alkaline Phosphatase	Urea
Sodium	Bilirubin (Total)	Bilirubin (Direct) (only if Total is	AST
		elevated)	
Bicarbonate	Magnesium	Lipase (reflex if Amylase is	Amylase
		> 2X ULN)	

9.2.5.4. Urinalysis

Urinalysis

Bilirubin, Glucose, Protein, Blood and Ketones, Leukocytes, Nitrites, pH, Specific Gravity and Urobilinogen by dipstick

Microscopic examination (if blood or protein is abnormal)

Microbiology (at discretion of Investigator based on urinalysis results)

9.2.5.5. Other Tests

Other Tests

NT-proBNP

Urine Creatinine (for calculation of 5-HIAA) at each 5-HIAA collection time

Estimated Glomerular Filtration Rate (eGFR)

FSH (as needed at Screening for confirmation of postmenopausal status)

Serum beta-hCG (pregnancy test; only at Screening)

Human Chorionic Gonadotropin (hCG) by urine dipstick

Pharmacogenetic sample

Sample for Future Research sample

Drugs of abuse: amphetamines, barbiturates, benzodiazepines, cocaine metabolites, methadone, opiates, phencyclidine, propoxyphene (only at Screening)

The Investigator must review the laboratory report, document this review, and record any clinically relevant changes occurring during the study in the AE section of the eCRF. The laboratory reports must be filed with the source documents. Clinically significant abnormal laboratory findings are those which are not associated with the underlying disease, unless judged by the Investigator to be more severe than expected for the patient's condition.

All laboratory tests with abnormal values considered clinically significant during participation in the study or within 4 weeks after the last dose of IP should be repeated until the values return to normal or baseline or are no longer considered clinically significant by the Investigator or Medical Monitor.

If such values do not return to normal/baseline within a period of time judged reasonable by the Investigator, the etiology should be identified, and the sponsor notified.

All protocol-required laboratory assessments must be conducted in accordance with the laboratory manual and the SoA (Section 1.3, Section 1.4, and Section 1.5).

If laboratory values from non-protocol specified laboratory assessments performed at the institution's local laboratory require a change in patient management or are considered clinically significant by the Investigator (e.g., SAE or AE or dose modification), then the results must be recorded in the eCRF.

Additional unscheduled laboratory assessments may be conducted at any time during the study if the Investigator or Sponsor deems it necessary for the safety of the patient.

9.2.6. Pharmacogenetic Testing

A separate and specific informed consent form will be provided to patients to allow the sponsor to obtain and test a patient's blood sample taken at the Baseline/Day1 and the Week 24 visits for pharmacogenetic markers that may be predictive of the natural history of the disease, response to therapy and tolerability of therapy. If it is not collected at the Baseline/Day 1 visit, it may be collected at any time during the treatment period. Providing these blood samples is optional and not required for participation in the study.

9.2.7. Optional Blood Sample for Future Research

In addition to the study-specific informed consent to be signed by each patient participating in the study, a separate, specific signature will be required to document a patient's agreement to provide additional samples or to allow the use of the remainder of their already collected biomarker specimens for optional non-genetic future research, once approved by local authorities as applicable according to specific local regulations. The specimens collected for optional future research will be used to increase our knowledge and understanding of the biology pathogenesis, progression and/or treatment outcomes, including efficacy, AEs, and the process of drug absorption and disposition.

A plasma sample will be obtained from all patients at the Day 1/Baseline visit and at the end of the treatment or ET (as applicable) visit of the Main Study for future research use. Samples will be collected and archived by the sponsor for up to 10 years.

9.2.8. Suicidal Ideation and Behavior Risk Monitoring

Rodatristat ethyl acts to decrease peripheral 5-HT levels and it was designed to not cross the blood-brain barrier; therefore, CNS 5-HT levels are not expected to be significantly impacted. However, patients being treated with IP should be monitored appropriately and observed closely for suicidal ideation and behavior or any other unusual changes in behavior, especially at the beginning and end of the course of treatment, or at the time of dose changes, either increases or decreases. IP in patients who experience signs of suicidal ideation or behavior following a risk assessment (see Section 8.1) must be stopped.

Screening and Baseline assessments (within 1 month) of suicidal ideation and behavior as well as potential treatment-emergent suicidal ideation and behavior will be monitored during the study using the C-SSRS.

Suicidal ideation and behavior as well as mood and anxiety assessments, as detailed below, will be obtained at time points indicated in the SoA in (Section 1.3).

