10 Selexipag and ACT-333679 PK (for subjects using selexipag at baseline only): At Day 1 and Week 4, a predose PK sample will be collected (patients will take selexipag in the clinic at these visits, and the PK samples will be collected approximately 12 h after the prior dose) Additional unscheduled safety assessments may be conducted at any time during the study if the Investigator or Sponsor deems it necessary for the safety of the

Clinical Study Protocol Altavant Sciences GmbH

HADS = Hospital Anxiety and Depression Scale; HR = heart rate; IP = investigational product; IRT = interactive response technology; LFTs = liver function tests; mo = months; NT-proBNP = N-terminal pro-brain natriuretic peptide; OLE = Open-Label Extension; PAH = pulmonary arterial hypertension; PAH-SYMPACT = Pulmonary Arterial Hypertension Symptoms and Impact Questionnaire; QIDS-C = Quick Inventory of Depressive System-Clinician Rated; RHC = right heart catheterization; RR = respiratory rate; Abbreviations: 5-HIAA = 5-hydroxyindoleacetic acid; 6MWT = 6-minute walk test; AEs = adverse events; BMI = body mass index; BP = blood pressure; C-SSRS = Columbia-Suicide Severity Rating Scale; D = day; ECG = electrocardiogram; ET = early termination; FSH = follicle stimulating hormone; FU = follow up; SAE = serious adverse event; temp = temperature; WHO FC = World Health Organization Functional Class; Wk = week

Schedule of Assessments – Open-Label Extension – (Post 24 Weeks of the Open-Label Extension) 1.5.

	Pregnancy Test	Clinic Visits ⁴	Follow Up ⁴
			(T weeks after last uest of
Week	Every 4 Weeks (+/- 2 days)	Every 24 Weeks (+/- 4 days)	
IP Dispensing via IRT ¹		X	
IP Compliance/ Accountability ²		X	
Concomitant medications	X	X	
Vital Signs (BP, HR, RR, temp, oxygen saturation)		X	X
Pregnancy Test (serum/urine) ³	X	X	X
Laboratory - Hematology, Coagulation, Chemistry (including LFTs)		X	X
Adverse Events	X	X	X

¹ As necessary, 6-month supply of IP will be dispensed.

Additional unscheduled safety assessments may be conducted at any time during the study if the Investigator or Sponsor deems it necessary for the safety of the

² Patients should be instructed to bring their used, partial, and unused IP containers with them to every Clinic Visit to assess compliance and IP accountability.

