³ Pregnancy test will be required every 4 weeks, in women of childbearing potential only. Urine pregnancy kits will be provided to the patient. Completion of the pregnancy test, and collection of adverse events and concomitant medications will be documented via telephone contact. Serum pregnancy test to be done to confirm a positive urine test. Additional pregnancy tests should be completed anytime menstruation is delayed and in women with infrequent or irregular menstrual cycles.

⁴ If a patient discontinues IP for any reason a follow-up visit must be performed 4 weeks after the last dose of ID.

Abbreviations: BP = blood pressure; HR = heart rate; IP = investigational product; RT = interactive response technology; LFTs = liver function tests; RR = respiratory rate; temp = temperature

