7.4. Open-Label Extension Design

Patients in the Main Study that do not discontinue prematurely and complete up to and including the Week 24 Visit, have the option to rollover into the OLE. Patients who continue into the OLE will be blinded to the treatment they received in the Main Study. Patients who received active IP in the Main Study will remain on their regimen. Patients randomized to placebo in the Main Study will be re-randomized to one of the 2 active rodatristat ethyl treatment arms (300 mg BID or 600 mg BID) in the OLE.

Patients who participate in the OLE will continue to receive rodatristat ethyl for 6.5 years, until the Investigator or patient chooses to stop the IP, any stopping criteria in the Main Study are met, IP becomes commercially available, or the Sponsor stops the study for lack of efficacy or a safety signal (whichever preceding criteria comes first). In no case will a patient be allowed to exceed 10 years of exposure unless the product is approved for a chronic indication.

During the OLE patients will be followed by the Investigator according to clinical practice, with formal (per protocol) safety assessments. These safety assessments will include AEs, clinical laboratory tests, vital signs, and concomitant medications. Female patients of childbearing potential will be required to use 2 reliable methods of contraception to reduce the risk of pregnancy during the course of the study and for at least 30 days following the last dose of rodatristat ethyl.

During the first 24 weeks of the OLE patients, will also undergo efficacy assessments. These efficacy assessments will include 6MWT, RHC, echocardiogram, WHO FC, and plasma NT-proBNP level. Urine pregnancy tests will be performed every 4 weeks in women of child-bearing potential only, while the patient is on IP and once at 4 weeks post dose. If there is not a clinic visit, a urine pregnancy test will be sent home with the patient and results will be followed up with a phone call. Additional pregnancy testing in women whose menstruation is delayed or who have infrequent or irregular menstrual cycles should be conducted as warranted.

See SoA in Section 1.4 and Section 1.5.

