7.12. Criteria for Investigational Product/Study Termination

All criteria for IP and study termination are the same as in the Main Study and can be found in Section 8.

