8.1. Discontinuation of Investigational Product

The Medical Monitor should be notified of any change to background PAH therapy to determine any need for withdrawal. See Section 8.2 for study withdrawal procedures.

Patients meeting any of the following liver chemistry criteria must be withdrawn (IP should be discontinued immediately) from the study by the Investigator:

- ALT or AST > 3X ULN and TBL > 1.5X ULN or INR > 1.5
- ALT or AST > 3X ULN with the appearance of fatigue, nausea, vomiting, right upper quadrant pain or tenderness, fever, rash, and/or eosinophilia (> 5%)
- ALT or AST > 5X ULN for more than 2 weeks
- ALT or AST >8X ULN

If liver chemistry tests meet any of the above criteria, repeat testing should be performed within 48 to 72 hours and the patient followed until resolution.

Patients meeting any of the following confirmed QT/QTc-related criteria must be withdrawn from the study by the Investigator:

- QTcF interval > 500 ms
- QTcF interval > 480 ms AND increase from Baseline ≥ 60 ms
- QTcF interval > 480 ms associated with syncope, life-threatening arrhythmias, resuscitated cardiac arrest, or seizure

The Investigator must also discontinue/withdraw a patient's participation in the study if any of the following criteria apply:

- Pregnancy
- Significant protocol violation/lack of compliance with the study and/or study procedures non-compliance with IP for discontinuation of patient is defined as < 50%.
- Severe constipation (e.g., obstipation with manual evacuation indicated) and/or severe, persistent, or worsening abdominal pain
- Any significant worsening on postdose C-SSRS indicative of active suicidal ideation with intent to act (defined as C-SSRS Suicidal Ideation category score of 4 or 5) or behavior (either preparatory acts/behavior, aborted attempt, interrupted attempt, or actual attempt)
- Severe depression or anxiety based on a HADS Depression or Anxiety score ≥ 15, or a QIDS-C Total Score ≥ 16.

• Any severe psychiatric or CNS AE as determined by the Investigator.

The Investigator may discontinue/withdraw a study patient's participation in the study if any of the following criteria apply:

Protocol RVT-1201-2002

Effective: 19JAN2022

• Behavioral or administrative reason

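### After OLE Week 24 no C-SSRS, HADS or QIDS-C is scheduled, although the mandatory withdrawals defined by those scales stay in force

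*Protocol*

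**What the plan says.** All references are to the protocol.

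- **Stopping rules in the OLE.** Section 7.12: "All criteria for IP and study termination are the same as in the Main Study and can be found in Section 8".
- **What those rules contain.** Section 8.1 obliges the investigator to withdraw a patient who worsens on the C-SSRS in a way "indicative of active suicidal ideation with intent to act (defined as C-SSRS Suicidal Ideation category score of 4 or 5") or of suicidal behavior. It obliges the same for "Severe depression or anxiety based on a HADS Depression or Anxiety score" of 15 or more, or a QIDS-C total of 16 or more.
- **First 24 OLE weeks.** Section 1.4 schedules all three scales at Weeks 4, 12, 18 and 24 and at early termination.
- **Afterwards.** Section 1.5, headed "Post 24 Weeks of the Open-Label Extension", has rows for drug dispensing, compliance, concomitant medication, vital signs, pregnancy test, laboratory tests and adverse events. None of the three scales has a row.
- **Text on OLE safety.** Section 7.4: "These safety assessments will include AEs, clinical laboratory tests, vital signs, and concomitant medications".
- **Duration.** Section 7.4: "Patients who participate in the OLE will continue to receive rodatristat ethyl for 6.5 years", unless one of several earlier stopping points is reached.
- **Monitoring intent.** Section 9.2.8 asks for close observation, "especially at the beginning and end of the course of treatment, or at the time of dose changes, either increases or decreases". In a separate paragraph it says the C-SSRS will be used to monitor ideation and behavior during the study. For timing of the scales it cites only Section 1.3.

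**The concern.** The plan keeps withdrawal thresholds but stops scheduling the instruments on which they are read. A HADS or QIDS-C cut-off cannot be crossed if the scale is not given, and the C-SSRS criterion needs someone to ask the questions. After OLE Week 24 these mandatory stops therefore apply only when suspicion has already prompted an unscheduled assessment.

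The end of treatment shows the contrast. A patient who stops at OLE Week 20 has a C-SSRS scheduled at the early-termination visit. One who stops at OLE Week 60 has a Follow-Up visit 4 weeks after the last dose, with no scale scheduled there.

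What is at stake is patient safety and the quality of long-term safety information. The benefit/risk table in Section 2.3 offers the scale-based withdrawals as the mitigation for mood disturbance. Section 9.3.1 names mood disturbance as an adverse event of special interest, and Section 7.2 makes long-term safety part of the OLE objective.

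**Working it through.** **1. Is it a lost table row?** Three other places agree with the reading of Section 1.5.
- The list of OLE safety assessments in 7.4 omits the scales too.
- The abbreviation list under 1.5 defines none of them, whereas those under 1.3 and 1.4 define all three.
- The last paragraph of 9.2.1 says the time points for all safety assessments are in 1.3, 1.4 and 1.5. Section 7.8 says OLE assessments are performed as in the Main Study, but it refers their schedule to 1.4 and 1.5, so it restores nothing.

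**2. How long is the uncovered period?** Inputs: 6.5 years maximum (7.4); 24 weeks covered by 1.4; clinic visits every 24 weeks thereafter (1.5).
- Maximum OLE: 6.5 × 365.25 = 2374.1 days; ÷ 7 = 339.2 weeks.
- After Week 24: 2374.1 − 168 = 2206.1 days; ÷ 7 = 315.2 weeks; ÷ 365.25 = 6.04 years.
- Share of the maximum OLE: 2206.1 ÷ 2374.1 = 92.9%.
- Clinic visits at Weeks 48, 72, …, 336: (336 − 48) ÷ 24 + 1 = 13, plus one Follow-Up.

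| OLE period | Scheduled occasions with the scales |
|---|---|
| Weeks 1 to 24 | 4 on-treatment visits, plus early termination |
| After Week 24 | 0 of up to 13 clinic visits; 0 at Follow-Up |

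**3. Which psychiatric stops still work without a scheduled scale?**
- 8.1: a psychiatric or CNS event that the investigator judges severe.
- 9.2.8: signs of suicidal ideation or behavior following a risk assessment.
- The scale thresholds themselves, if an unscheduled assessment is done. The note under 1.5 allows this whenever the investigator or sponsor considers it necessary for safety.

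All three start from a problem that someone has noticed or that the patient has reported.

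**4. How often would a problem be noticed?** Section 9.3.3 prefers open, non-leading questions about adverse events, so suicidality is not asked about systematically. The 4-weekly contact in 1.5 is attached to pregnancy testing: "Completion of the pregnancy test, and collection of adverse events and concomitant medications will be documented via telephone contact". That test is for women of childbearing potential only, so other patients appear to be contacted every 24 weeks.

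**The case against.** The best defence is that this is a deliberate taper. Section 7.4 has OLE patients followed largely according to clinical practice. The amendment rationale for making the first 24 OLE weeks resemble the Main Study is that up to one-third of patients start active drug there, so intensive assessment is tied to first exposure. The OLE safety endpoints in 7.3.1 are proportions with adverse events or laboratory abnormalities, and none uses a scale. Sections 2.1 and 9.2.8 expect little effect on central serotonin. Patients are told to call if an adverse event occurs (7.8), and the IDMC's remit includes the OLE (10.5.1).

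Much of this stands. It explains a lighter schedule. It does not explain keeping mandatory thresholds while dropping the scales that define them, and the protocol gives no reason for that combination.

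Two stronger readings are tempting, and the documents do not support them.
- A reader might infer that 9.2.8 requires a C-SSRS at the end of treatment and at every dose change. It does not. The sentence naming those moments asks for clinical vigilance, the C-SSRS comes in a separate paragraph, and the Main Study schedules no scales at dose changes either.
- A reader might infer that psychiatric stopping is disabled after OLE Week 24. It is not, as step 3 of the working shows.

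**Conclusion.** The point holds as a gap between the retained stopping rules and the schedule. The loss is limited to routine screening of patients in whom no problem is suspected.

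The 6.0 years and 13 visits are maxima. They assume a patient who stays in the OLE for the full 6.5 years and is seen every 24 weeks; OLE treatment may end sooner for several stated reasons. The documents give no rate at which patients would cross a threshold, so none is estimated. The primary endpoint and the Main Study analyses are unaffected. It is worth correcting because the rule is mandatory, the risk is one the protocol itself names, and the remedy is cheap.

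**What to change.** - In Section 1.5, add the C-SSRS (Since Last Visit version), HADS and QIDS-C to the 24-weekly Clinic Visits column and to the Follow-Up column.
- Add the three scales to the list of OLE safety assessments in 7.4.
- Have 9.2.8 cite Sections 1.3, 1.4 and 1.5 for the timing of the scales. At present it cites 1.3 alone, which leaves out even the OLE time points that 1.4 already schedules.

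No threshold changes and no visit is added.

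The cost is one amendment with IRB/IEC approval before implementation (Appendix 5), at about 68 sites. It also means probably a few minutes (a judgement, not a figure from the documents) at up to 13 existing clinic visits and the Follow-Up per patient. The sites already use the scales, but C-SSRS rater training must be no more than 2 years old (9.2.8.1) and would have to be kept current through the OLE.

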9.2.8.1. Columbia Suicide Severity Rating Scale

The C-SSRS is a valid, reliable, evidenced-based suicidal ideation and behavior rating scale, which was developed by multiple institutions, including Columbia University with National Institute of Mental Health support, to evaluate suicide risk (CLP, 2016). The rater-/clinician-administered versions of the C-SSRS for research assess severity and intensity of suicidal ideation, types of suicidal behaviors, and lethality of suicide attempts at time points and over time periods that are typical for randomized control studies. The C-SSRS has been identified by the FDA (FDA, 2012) as acceptable for use in clinical research and has been used extensively in clinical studies throughout the U.S. and around the world.

Protocol RVT-1201-2002

Effective: 19JAN2022

Training should be completed by any study staff delegated to perform this assessment. Online training is available, and a certificate of completion is issued once the training is completed and must be filed at the site. Training must be current within the previous 2 years. The sign-up and training portal can be found at the following link:

https://cssrs.columbia.edu/training/training-research-setting/

An example of the C-SSRS can be found in Appendix 10.

9.2.8.2. Hospital Anxiety and Depression Scale

The HADS is a 14-item, self-rated measure designed to be used as a brief screen for depression (7 items) and anxiety (7 items) disorders among nonpsychiatric, medically ill, outpatient populations (Zigmond & Snaith, 1983). As a screening instrument, the HADS does not provide a definitive diagnosis, but is the first step in a multistage process of selecting individuals at elevated risk for disorder to be evaluated through clinical interview.

An example of the HADS can be found in Appendix 11.

9.2.8.3. Quick Inventory of Depressive Symptomatology

The 16-item QIDS (Rush et al., 2003) is designed to assess the severity of depressive symptoms. The QIDS is available in the clinician-rated (QIDS-C) and self-reported versions (QIDS-SR). Both versions assess all the criterion symptom domains designated by the American Psychiatry Association Diagnostic and Statistical Manual of Mental Disorders - 4th edition (DSM-IV) (APA, 1994) and the 5th edition adds reference to diagnose a major depressive episode. The QIDS-C version will be used in this study. The QIDS-C is sensitive to change with medications, psychotherapy, or somatic treatments, making it useful for both research and clinical purposes. The psychometric properties of the QIDS-C have been established in various study samples.

An example of the QIDS-C can be found in Appendix 12.

9.3. Adverse Events, Adverse Events of Special Interest, and Serious Adverse Events

The definitions of an AE or SAE can be found in Appendix 14.

AEs will be reported by the patient (or, when appropriate, by a caregiver, surrogate, or the patient's legally authorized representative).

The Investigator and any qualified designees are responsible for detecting, documenting, and recording events that meet the definition of an AE or SAE and remain responsible for follow up of AEs that are serious, considered related to the IP or study procedures, or that caused the patient to discontinue the study (see Appendix 14).

